5.4 Safety Analysis

Incidence and rate of adverse events.

AEs and SEs will be summaries counting both the number of separate events and the number of subjects experiencing events occurring during the study period will be provided overall, per system organ class and preferred term by presenting.

Confidential & Proprietary

the unauthorized use, disclosure, distribution or copying of these information is strictly prohibitea

Furthermore, similar summaries will be provided stratified according to the seriousness, severity, and relationship to the study medication. The percentage of cases with an event will be analyzed and compared by the Chi-Square test. Mean changes in in vital signs and Laboratory variables, will be assessed by using student t-test for with in groups and analysis of variance for comparison between groups.

6. Listing of Tables

- Participant Disposition
- Demographical and baseline characteristics with comparison of demographical and baseline characteristics
- Profile of Medical History and clinical Examinations
- Changes in Vital Signs
- Comparison of Mean Time to Clinical Improvement (TTCI) using NEWS Score
- Comparison of Mean Time to Clinical Improvement (TTCI) using 7 point ordinal scale.
- Rate of progression to severe/critical COVID-19 disease based on NEWS score [Time frame: First treatment date up to 28 days
- Rate of progression to severe/critical COVID-19 disease based on 7point Ordinal scale [Time frame : First treatment date up to 28 days

Confidential & Proprietary

The unauthorized use, disclosure, distribution or copying of these information is strictly prohibited

- Mean Time to COVID-19 nucleic acid testing negativity in oropharyngeal/nasal swab) [Time Frame: First treatment date up to 28 days]
- Incidence of ICU
- Profile of subject survival rate
- Incidence of Mechanical ventilators
- Time to COVID-19 nucleic acid testing negativity in oropharyngeal/nasal swab) [Time Frame: Days 1, 7, 15]
- Percent of participants with worsening comorbid condition [Time Frame: First treatment date up to 28 days]
- Changes in clinical assessment of co morbid conditions
- Comparison of Changes Laboratory Variables
- Profile of adverse events in each group
- Profile of Serious adverse events in each group

7. Graphs

Individual Graphs for all Primary and secondary variables

8. Software

SPSS Version 10.0

Confidential & Proprietary

The unauthorized use, disclosure, distribution or copying of these information is strictly prohibited

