Study Population	
 • 50 years or older • Positive RT- PCR for Sars-Co-V2. • Either asymptomatic or have mild symptoms. Onset of symptoms within no more than 4days • With chronic stable medical conditions: Diabetes Mellitus, or Hypertension, or chronic heart disease.
Study Duration	Total study duration approximately 35 days Screening: 04 days Treatment duration: 14 days Follow-up: 14 days from end of treatment

Number of Sites	02 (two)
Treatment Duration	14 days
Treatment Arms	
Two treatment arms
 
 • Arm A: ViraCide softgels: 3 soft gels, two times every day after breakfast and dinner for 14 days+ SOC Therapy • Arm B: Placebo softgels: 3 soft gels, two times everyday after breakfast and dinner for 14 days + SOC Therapy
Purpose of the study	To study the effectiveness and safety of the Study Drug, ViraCide
	softgels by oral administration compared with placebo softgels in 50 years or older subjects with asymptomatic or mildly symptomatic coronavirus infection (COVID-19) and stable comorbidities.
Objectives	
Primary Objectives
 
1. To evaluate the efficacy of “ViraCide” in the management of mild COVID-19 disease
 
Secondary Objectives
 
1. To evaluate the safety of “ViraCide” in the management of mild COVID-19 disease

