	
Note:
 
*Hematology: Complete blood count (CBC); erythrocyte sedimentation rate (ESR)
 
*Biochemistry:
 
 • Random Blood Sugar, • Serum Creatinine • SGOT, SGPT • Alkaline Phosphatase • Bilirubin-Total/Direct/Indirect • Total Proteins/Albumin/Globulin/A:Gratio • Low density lipoprotein (LDL) Cholesterol(Direct) • LDH • Total Cholesterol • Triglycerides • High Sensitive C-reactive protein(HS-CRP) • BUN (Blood Urea Nitrogen) /Urea • Serum Calcium • Serum Sodium • Serum Potassium • Uric Acid 
*X-ray PA view is an optional test at screening. It may be done

	
at any other time during the study if deemed necessary by the Investigator
 
*Urine pregnancy test (for females only) at screening
 
Note: If subject is discharged before Day 15 PI's discretion as per patients health condition, then assessments scheduled for Day 15 will be carried out on the discharge day (as far as possible and those not performed will be noted on appropriate CRF page) and Day 15 visit will be done telephonically.

Standard of Care Therapy	
SOC therapy for coronavirus infection (COVID-19, SARS-CoV-2) has not been developed yet. Treatment will be given as per the discretion of the PI or as per the guidelines issued by the GOI. GOI guidelines can be accessed here: https://www.mohfw.gov.in/

Concomitant Medications Allowed by the Protocol	
 1. Medications for Diabetes Mellitus 2. Medications for hypertension 3. Statins 4. Blood thinners like aspirin at PI discretion 5. Any medication deemed necessary by the PI to manage the AE/SAE 6. Any other medication deemed necessary by the PI to manage a comorbid condition that is not likely to affect the treatment Protocol
Prohibited Concomitant Medications	Any other herbal medicine or dietary supplement
Statistical Analysis	
Sample size of total 112(56 cases in each arm) completed cases needed to assess the study objective at 80% power and 5% level of significance.
 
Considering 10 % dropout total 124 (62 cases in each arm) cases will be enrolled in this study.

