5. Time to COVID-19 nucleic acid testing negativity in oropharyngeal/nasal swab) [Time Frame: First treatment date up to 28 days]

Confidential & Proprietary

The unauthorized use, disclosure, distribution or copying of these information is strictly prohibited

Secondary Efficacy Endpoints:

1. Incidence of ICU admissions [Time Frame: 28 days]
2. Subject survival rate [Time Frame: 28 days]
3. Incidence of mechanical ventilation [Time Frame: First treatment date up to 28 days]
4. Time to COVID-19 nucleic acid testing negativity in oropharyngeal/nasal swab) [Time Frame: Days 1, 7, 15]
5. Change in clinical or laboratory assessment of comorbid condition [Time Frame: First treatment date up to 28 days]
6. Percent of participants with worsening comorbid condition [Time Frame: First treatment date up to 28 days]

Safety Endpoints

1. Proportion of subjects in the treatment arm who had AE, SAE
2. Proportion of subjects in the placebo arm who had AE, SAE

Confidential & Proprietary

Any unauthorized use, disclosure, distribution or copying of these information is strictly prohibited

3 Analysis sets

Per protocol subset (PP)

Subjects without any Major protocol violation would be included in the per-protocol population, including those subjects who have completed all the visits, who did not take any prohibited medications during the study period and whose CRF was completed as requested.

Modified Intention to treat subset (mITT)

The term “mITT” includes all randomized subjects who met all inclusion/exclusion criteria, administered at least one dose of assigned product with at least completed one visit will be included in the mITT population.

Safety analysis subset

The safety population will consist of all subjects enrolled in the study, who have received at least one dose of study products i.e. mITT population.

Methods of Analysis

Primary Efficacy and secondary endpoints will be analyzed using the PP & mITT population. And Safety variables as per mITT only.

4 Data Handling

Data entry into CRF must be performed as per general CRF data entry guidelines, summarized at the time of data entry feasibility training. Data entry will be made as per source document without interpretation or modification to maintain consistency and accuracy of the data. Study specific

Confidential & Proprietary

Any unauthorized use, disclosure, distribution or copying of these information is strictly prohibited

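### SAP 5.4 compares adverse-event percentages between arms only by a chi-square test, with no risk difference, no confidence interval and no statement of how a non-significant result will be read

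*SAP*

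**What the plan says.** The protocol synopsis has one secondary objective: "To evaluate the safety of “ViraCide” in the management of mild COVID-19 disease". SAP section 2 serves it with two safety endpoints, one per arm. The first reads "Proportion of subjects in the treatment arm who had AE, SAE"; the second is the same for placebo. No between-arm hypothesis is attached to either.

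SAP 5.4 contains three pieces of safety analysis:

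- **Descriptive AE tables.** Numbers of events and of subjects are given overall and by system organ class and preferred term, and "similar summaries will be provided stratified according to the seriousness, severity, and relationship to the study medication".
- **A between-arm test on events.** "The percentage of cases with an event will be analyzed and compared by the Chi-Square test".
- **Vital signs and laboratory changes.** These are analysed by "student t-test for with in groups and analysis of variance for comparison between groups".

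The SAP mentions a 95% confidence interval only alongside the mean and standard deviation of continuous summaries (5.1 and 5.2). The list of tables in section 6 has an AE profile and an SAE profile by group, with no estimate of the difference. On size, the synopsis says "Sample size of total 112(56 cases in each arm) completed cases needed to assess the study objective at 80% power and 5% level of significance", raised to 62 per arm for dropout. It gives no expected AE rate and no power for any safety comparison.

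**The concern.** A chi-square test returns a p-value. It does not show how large an excess of harm the data are compatible with, and that is what a reader needs in order to judge safety. When events are uncommon and there are about 60 subjects per arm, p > 0.05 is a likely result even when the true excess matters. The SAP does not say how that result will be worded, so a report that follows the plan could state that AEs did not differ significantly and stop there.

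What is at stake is the answer to the trial's only secondary objective, in subjects aged 50 or older with diabetes, hypertension or chronic heart disease.

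**Working it through.** **Inputs.** From the documents: 56 completers and 62 enrolled per arm, 1:1 allocation, 5% significance level. Assumed, because the documents are silent: a two-sided test, no continuity correction, and all event rates. The number analysed cannot exceed 62 per arm. It may be lower, because SAP section 3 equates the safety set with the mITT set, which also requires eligibility and a completed visit.

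**The plan's own figure.** 112 × 1.10 = 123.2, rounded up to 124, or 62 per arm, so the dropout step reproduces. The 112 itself cannot be recomputed, because no endpoint, effect size or event rate is given.

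**Power of the planned test, 10% versus 20% (assumed).** Normal approximation, with p̄ the average of the two rates:

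power = Φ{ [ |p2 − p1| − 1.96·√(2p̄(1 − p̄)/n) ] / √( [p1(1 − p1) + p2(1 − p2)]/n ) }

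- n = 62: √(2 × 0.15 × 0.85/62) = 0.0641 and √((0.09 + 0.16)/62) = 0.0635. Then (0.10 − 0.1257)/0.0635 = −0.405, so power is 34.3% and the miss rate 65.7%.
- n = 56: the two terms are 0.0675 and 0.0668. Then (0.10 − 0.1323)/0.0668 = −0.483, so power is 31.5% and the miss rate 68.5%.

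Enumerating every pair of binomial outcomes, and rejecting when the pooled |z| exceeds 1.96, gives miss rates of 66.4% and 68.3%. With a continuity correction or Fisher's test they are 74.1% and 77.5%. Power of 80% for this contrast would need 199 per arm.

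**Dependence on the assumed rates.** Miss rates by exact enumeration, uncorrected chi-square:

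| Placebo vs ViraCide (assumed) | 62 per arm | 56 per arm |
|---|---|---|
| 2% vs 8% | 68% | 71% |
| 5% vs 10% | 82% | 84% |
| 5% vs 15% | 53% | 57% |
| 10% vs 20% | 66% | 68% |
| 10% vs 30% | 19% | 22% |
| 20% vs 30% | 75% | 77% |
| 20% vs 40% | 31% | 35% |
| 30% vs 60% | 6% | 10% |

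The test does well for a large excess in common events and poorly for uncommon events, the range in which SAEs might be expected.

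**What an interval would add.** Newcombe's interval for d = p1 − p2 uses the Wilson limits (l, u) of each arm: lower = d − √[(p1 − l1)² + (u2 − p2)²], upper = d + √[(u1 − p1)² + (p2 − l2)²]. For illustrative tables, ViraCide first:

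- 13/62 vs 6/62 with an AE: 21.0% (12.7 to 32.6) vs 9.7% (4.5 to 19.5). Chi-square p = 0.08. The difference is +11.3 points, 95% interval −1.6 to +24.1.
- 5/62 vs 1/62 with an SAE: 8.1% vs 1.6%. Chi-square p = 0.09. The difference is +6.5 points, 95% interval −1.9 to +16.0.
- 0/62 in one arm: the exact upper 97.5% bound on that arm's rate is 1 − 0.025^(1/62) = 5.8%.

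In the first two tables the planned test is non-significant, yet the data do not exclude an excess of 24 or 16 points.

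**The case against.** A reader might infer that safety as a whole is judged only by this chi-square test. It is not. SAP 5.4 also plans a between-group analysis of variance on vital signs and laboratory changes, and AE tables by seriousness, severity and relationship. The point is confined to between-arm inference on AE and SAE percentages, though those are the named safety endpoints.

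A reader might also infer that the plan will treat p > 0.05 as proof of safety. No passage says so. The endpoints are listed one arm at a time without a hypothesis, so a descriptive reading is natural. The defect is silence on interpretation, not a wrong rule.

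Nor can the trial be faulted for failing an 80% power target on safety: the synopsis states that power for an unspecified study objective and claims none for AEs. A trial of 124 subjects that is underpowered for AEs is ordinary. Harm would not always be missed either; at 10% versus 30% or 30% versus 60% the test would usually detect it.

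Finally, the planned subject counts would let a careful reader calculate the difference and its interval, and the omission biases no estimate. That limits the seriousness of the point but does not remove it. The interval belongs in the sponsor's own report, fixed in advance, and a published p-value without it invites the wrong reading.

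**Conclusion.** The point stands in this limited form. AE and SAE percentages are compared between arms only by a p-value, with no estimate of the difference and no statement of what a non-significant result means. On an assumed 10% versus 20%, an uncorrected two-sided 5% test misses the doubling about two times in three, and about three times in four with a continuity correction or Fisher's test. The figure depends heavily on the assumed rates: across the doublings examined it runs from 82–84% (5% versus 10%) to 6–10% (30% versus 60%). The case for reporting an interval does not depend on any of these rates or on the chi-square variant used. This is an inexpensive improvement that should be made, because it changes what the trial can say on its only secondary objective.

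**What to change.** In SAP 5.4, for subjects with (a) any AE, (b) any SAE, (c) any treatment-related AE and (d) any AE leading to study-drug withdrawal:

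1. Report n/N per arm and the ViraCide-minus-placebo risk difference with a two-sided 95% Newcombe or Miettinen–Nurminen interval.
2. Where an arm has no events, add the exact upper bound for that arm's rate.
3. Keep the chi-square p-value as descriptive only.
4. State that a non-significant test will not be interpreted as evidence of safety or of no difference, and word the conclusion from the upper limit of the interval.

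Add matching columns to the AE and SAE tables in SAP section 6. No formal safety margin is needed.

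The cost is SAP wording and a few table columns, with no extra data or subjects. The downside is a less favourable safety statement. Even if both arms had a 10% AE rate (assumed), the simple Wald half-width at 62 per arm would be 1.96 × √(2 × 0.10 × 0.90/62) = 10.6 points.

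### Laboratory safety is analysed only through mean changes, which average away one to three subjects with a very large rise; no subject-level laboratory summary is planned.

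*SAP*

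**What the plan says.** Safety is the sole secondary objective in the Protocol synopsis: "To evaluate the safety of “ViraCide” in the management of mild COVID-19 disease".

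SAP section 5.4 gives one method for laboratory values: "Mean changes in in vital signs and Laboratory variables, will be assessed by using student t-test for with in groups". The two arms are compared by ANOVA on the same changes. SAP section 6 lists one matching table, "Comparison of Changes Laboratory Variables". Neither section names a shift table, a count of subjects beyond a limit, laboratory grading, a listing of abnormal values or a rule for multiple tests.

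The subject-level safety comparison in SAP 5.4 is for adverse events: "The percentage of cases with an event will be analyzed and compared by the Chi-Square test". Adverse events are also tabulated by organ class and preferred term, and by seriousness, severity and relationship to study medication.

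The Protocol synopsis (Laboratory Investigations) schedules chemistry at screening and Day 15, with no laboratory tests on Days 1 and 7. If a subject is discharged before Day 15, the Day 15 assessments move to the discharge day as far as possible, and those not done are recorded as such.

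**The concern.** A mean-change test asks whether the whole arm has shifted. It is a poor tool when the safety question is whether a few individuals had a marked rise in, for example, SGPT or creatinine. Those few add little to a mean over 62 subjects and much to its SD.

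The population is aged 50 or older with diabetes, hypertension or chronic heart disease, and takes other medicines. Severe liver and renal disease are excluded at entry, so a new abnormality relative to screening can be interpreted. As planned, the laboratory section of the report could say that no mean change was significant while the tables showed nothing of two or three marked rises in the active arm. The same plan runs one test per laboratory value with no statement on how to read isolated small p-values.

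**Working it through.** **Inputs**
- Arm size, from the Protocol synopsis (Statistical Analysis): "Sample size of total 112(56 cases in each arm) completed cases needed" and "Considering 10 % dropout total 124 (62 cases in each arm) cases will be enrolled in this study".
- Significance level: the 5% appears only in the sample-size statement, "at 80% power and 5% level of significance". SAP 5.4 gives no level for safety tests, so two-sided 5% is assumed here.
- SD of laboratory change and size of a large rise: not in the documents. Assumed range: affected subjects rise by 3 to 20 SDs of the ordinary change.
- Number of chemistry values: counted from the Protocol's biochemistry list.

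**1. The plan's own figure.** 112 × 1.10 = 123.2, rounded up to 124, or 62 per arm. Dividing by 0.90 instead gives 124.4, rounded up to 125. The difference is immaterial here. The 112 cannot be rebuilt because no effect size is stated. The safety set is the treated population, so laboratory data should come from about 56 to 62 per arm.

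**2. What a few large rises do to t.** Let k of n active subjects rise by D, in units of the ordinary SD. With two arms, ANOVA on change is the two-sample t test. Its central value is about

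t = (kD/n) / √{ [2 + D²·k(n−k)/(n(n−1))] / n }.

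This increases with D towards a ceiling of √[k(n−1)/(n−k)], in which D and the SD no longer appear. For n = 62:

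| k | Ceiling of t | p at the ceiling | t at D = 10 |
|---|---|---|---|
| 1 | √(61/61) = 1.00 | 0.32 | 0.67 |
| 2 | √(122/60) = 1.43 | 0.16 | 1.12 |
| 3 | √(183/59) = 1.76 | 0.08 | 1.47 |
| 4 | √(244/58) = 2.05 | 0.04 | 1.78 |

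The critical value on 122 degrees of freedom is 1.98, so four affected subjects are needed before even the ceiling passes it. At n = 56 the ceilings are 1.00, 1.43, 1.76 and 2.06.

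**3. Simulation.** The proportion of trials significant in the direction of harm, for rises of 3 to 20 SD at 56 and 62 per arm (20,000 runs per setting), was 1-5% for one subject, 4-9% for two and 8-18% for three. A separate simulation with 62 per arm, a rise of 200 U/L in SGPT and an assumed SD of 10 to 30 U/L gave 1-5%, 4-9% and 15-19%. Across both, the range for three subjects is 8-19%.

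Larger rises do not help. With SGPT reaching ten times an assumed upper limit of 40 and an SD of about 10, the figures were 0%, 0.1-0.3% and 7-8%. The within-group t test reached at most 18%. A Mann-Whitney test gave about 5% for one subject and 7% for three.

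**4. Chance findings.** Counting SGOT and SGPT separately, bilirubin as 3, proteins as 4 and BUN/urea as 1 gives 22 chemistry values; counting bullets gives 16. Expected between-arm false positives in either direction are 22 × 0.05 = 1.1 or 16 × 0.05 = 0.8, whatever the correlation. In the direction of harm only, 22 × 0.025 = 0.55.

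**5. What a count would give.** For 1, 2 or 3 of 62 versus 0 of 62, Fisher's p is 1.00, 0.50 and 0.24. For 3 versus 0 the difference is 3/62 = 4.8 percentage points. The Wilson limits are 1.7% to 13.3% for 3/62 and 0% to 5.8% for 0/62. The Newcombe 95% interval is then 4.8 − √(3.2² + 5.8²) to 4.8 + √(8.4² + 0²), or about −1.8 to 13.3 points. It includes zero, but the three cases are on the page.

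**The case against.** **The adverse event tables may catch these cases.** This is the strongest reply. The named safety endpoints are the proportions of subjects with AEs and SAEs, and SAP 5.4 tabulates these by subject. A large rise that an investigator reports as an AE would appear there as an individual case, and laboratory reports are in the CRF. A reader might infer that the plan would miss laboratory toxicity altogether; the documents do not support that. What remains is that they nowhere say when an abnormal value becomes an AE, so this route depends on each investigator's judgement.

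**Other parts of the SAP could be read as covering this.** SAP 5.1 mentions a chi-square test for categorical data and changes during follow-up, but under demographic and baseline information, with no laboratory category or table attached. The secondary endpoint on laboratory assessment concerns the comorbid condition, and SAP 5.3 gives it no threshold for liver or kidney values.

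**Counts are no more significant than means.** This stands in full. A reader might take the low detection rates as showing a power gain from counting. Step 5 shows there is none to speak of; what improves is visibility.

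**The multiplicity point is the weaker half.** This stands in part. It is tempting to quote 1 − 0.95²² = 68% as the chance of at least one false signal, but that needs 22 independent tests, and the bilirubin and protein values are linked. The 5% per test is itself an assumption, and leaving safety parameters unadjusted is common. Only the expected number, about one, should be used.

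**Conclusion.** The point holds as a gap in the laboratory safety analysis. The one stated method averages away one to three very large individual rises, and the SAP names no laboratory output that would show them. The ceiling on t (about 1.0, 1.4 and 1.8) is algebra and needs no assumed SD. The detection rates (roughly 1-5%, 4-9% and 8-19%) rest on two-sided 5% and rises of 3 to 20 SD. The expected count of about one chance difference (0.8 to 1.1) rests on 5% per test and on how the panel is counted.

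A reader might conclude that the trial's safety conclusion will be wrong in both directions. The documents do not go that far: they do not make a laboratory p-value decisive, and reported AEs are summarised by subject. The laboratory section could mislead, and the remedy is cheap, so the change should be made. It does not affect the efficacy analysis.

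**What to change.** In SAP 5.4 and section 6, make the lead laboratory safety output, per arm:

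- a shift table from screening to Day 15 or discharge (low, normal or high against the laboratory's reference range), showing the number missing per arm because some discharge-day tests may not be done;
- the number of subjects newly above multiples of the upper limit for SGOT, SGPT, bilirubin and creatinine, with the between-arm difference and 95% CI. The sponsor should set the multiples before unblinding.

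Keep the mean-change table, but label its p-values descriptive.

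The cost is SAP wording and one or two extra tables from data already collected, with no new visits, samples or subjects.

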Visits of Assessment	
Screening and 3 visits and one telephonic follow-up
 
Screening Inclusion/Exclusion Criteria, Subject Inform Consent, Demography, Medical History, Physical Examination, Vital Signs, HIV; HBsAg; HCV; Hs-CRP; Pulse oximetry; NEWS scoring; 7- point ordinal scoring; Medication list review (medications being taken for comorbid conditions), Lab assessment; Urine analysis Note: Patients who do not meet the study inclusion exclusion criteria during screening should not be randomized into the study.
 
Day 1 Randomization, Vital Signs, Pulse oximetry, AE/SAE, Concomitant Medication, ViraCide/ Placebo treatment start, NEWS scoring; 7-point ordinal scoring
 
Day 7 Physical Examination, Vital Signs, AE/SAE, Concomitant Medication, ViraCide/ Placebo Compliance check, Pulse oximetry; NEWS scoring; 7-point ordinal scoring. (Note: If the subject is discharged on this day as per PI's discretion and patient's health condition then assessment scheduled for day 15 will be carried out on discharge day).
 
Day 15 Physical Examination, Vital Signs, AE/SAE, Concomitant Medication, ViraCide/ Placebo treatment end, RT-PCR for

	
Sars- Co-V2, Hs-CRP, Safety Lab Tests, Pulse oximetry; NEWS scoring; 7-point ordinal scoring, ViraCide/ Placebo Compliance check, Lab assessment including urine analysis
 
Day 28 Phone call follow up for time :
 
 • until negative RT-PCR for Sars-Co- V2, COVID-19 related mortality, • development of any COVID-19 symptom, • development of any worsening of comorbid condition; • Development of new AE/SAE; Resolution status of previous AE/SAEs 
Note: If subject is discharged before Day 15 on PI's discretion as per patients health condition, then assessments scheduled for Day 15 will be carried out on the discharge day (as far as possible and those not performed will be noted on appropriate CRF page) and Day 15 visit will be done telephonically.

Laboratory Investigations	
Screening: Recording RT-PCR- Sars-Co-V2 result; Urine pregnancy test; HIV; HBsAg; HCV; Hs-CRP; Hematology* + Biochemistry + Urine analysis*; ECG
 
Day 1: No labs
 
Day 7: No labs
 
Day 15: Oropharyngeal/nasal swab for PCR- Sars-Co-V2; Hematology* + Biochemistry + Urine analysis*; ECG; Serological biomarker: Hs-CRP

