5.1 Descriptive methods

Participant Disposition

Demographic and Baseline Information

Continuous variables that are Age, weight, BMI, and other demographical characteristics will be summarized by overall using summary statistics i.e. the number of observations, mean and standard deviation with 95% CI (among normal distribution) or median with range (if non-normal distribution). Categorical values like gender and clinical Examination will also be summarized using frequencies and percentages.

Confidential & Proprietary

Any unauthorized use, disclosure, distribution or copying of these information is strictly prohibited

The medical history and Physical examination will be presented using frequencies and percentages of subjects for the Safety population. For continuous data student analysis of variance test and for categorical data Chi square test will be estimated to compare the baseline demographical data between groups and changes during the follow up.

5.2 Efficacy Parameters:

Summary of efficacy parameters – the number of observations, mean and standard deviation with 95% CI (among normal distribution) or median with range (if non-normal distribution)

Analysis of Primary Efficacy Parameters

In this study median Time to Clinical Improvement (TTCI) using NEWS Score [Time Frame: First treatment date up to when PCR is negative] TTIC using 7-point ordinal scale [Time Frame: First treatment date up to when PCR is negative] will be assessed for both Test and Placebo group and compare the mean time between two arms by using Mann Whitney U test.

Other variables that are Rate of progression to severe/critical COVID-19 disease based on NEWS score and 7 point ordinal scale [Time frame: First treatment date up to 28 days] will be compared by using Chi Square test.

Other parameter like Time to COVID-19 nucleic acid testing negativity in oropharyngeal/nasal swab) [Time Frame: First treatment date up to 28 days] will be estimated by Student t test or one way analysis of variance. If data is

Confidential & Proprietary

Any unauthorized use, disclosure, distribution or copying of these information is strictly prohibited

not passing normality for continuous variable Mann Whitney test will be assessed instead of student t test.

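### SAP 5.4 compares laboratory and vital-sign changes between arms without using the baseline as a covariate; ANCOVA would be a free gain in precision (minor)

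*SAP*

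**What the plan says.** SAP section 5.4 (Safety Analysis) plans two kinds of test for changes in laboratory values and vital signs: "student t-test for with in groups and analysis of variance for comparison between groups". SAP section 5.1 (Descriptive methods) also names analysis of variance for continuous data, to "compare the baseline demographical data between groups and changes during the follow up". Neither section names a covariate, and the words ANCOVA, covariate and baseline adjustment appear in neither document.

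The baseline data exist. In the Protocol synopsis, the Laboratory Investigations row lists for Screening "HIV; HBsAg; HCV; Hs-CRP; Hematology* + Biochemistry + Urine analysis*; ECG", with no laboratory tests on Days 1 and 7. It then lists "Day 15: Oropharyngeal/nasal swab for PCR- Sars-Co-V2; Hematology* + Biochemistry + Urine analysis*; ECG; Serological biomarker: Hs-CRP". Under Visits of Assessment, vital signs are taken at Screening, on Day 1 ("Randomization, Vital Signs, Pulse oximetry, AE/SAE, Concomitant Medication") and again on Days 7 and 15. If a subject is discharged before Day 15, the Day 15 assessments move to the discharge day as far as possible.

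SAP section 2 lists among the secondary efficacy endpoints "Change in clinical or laboratory assessment of comorbid condition". SAP section 5.3 names a test for the clinical part of that endpoint and none for the laboratory part.

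**The concern.** A change score subtracts the whole baseline value, as if the slope of follow-up on baseline were exactly 1. When the slope is below 1, which is usual, this over-corrects. The difference between arms then carries avoidable noise, and any chance imbalance at baseline leaks into it with the opposite sign. ANCOVA estimates the slope from the data and removes both problems at almost no cost. SAP 5.1 plans to test baseline comparability, but the plan makes no adjustment if an imbalance appears.

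The within-arm t-tests are a second, smaller matter. They ask whether each arm changed over time, not whether the arms differ. One arm can reach significance and the other not when the true change is the same in both.

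At stake is the precision of the between-arm estimates for laboratory values and vital signs, and possibly of one secondary efficacy endpoint. No primary endpoint is affected.

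**Working it through.** **Inputs from the documents.** Allocation is 1:1 (Protocol, Study Design). There are 56 completers per arm, 112 in total, with 80% power and a 5% level (Protocol, Statistical Analysis).

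**Inputs assumed.** The correlation r between baseline and follow-up is not given and is shown from 0.3 to 0.9. Tests are taken as two-sided, because sidedness is not stated.

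**The plan's own figure.** The documents give no precision or power for the laboratory and vital-sign comparison, so there is nothing to reproduce for it. The overall sample size can be checked only at the dropout step: 112 × 1.1 = 123.2, rounded up to the stated 124. The 112 itself cannot be rebuilt, because no effect size is given. Worked backwards by the normal approximation, 56 per arm gives 80% power for a standardised difference of (1.960 + 0.842) × √(2/56) = 0.53. Only the 56 per arm is used below.

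**Variance of the arm difference.** Let s0 and s1 be the baseline and follow-up SDs. Up to the common factor 2/n:

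- change score: s0² + s1² − 2·r·s0·s1
- ANCOVA: s1²·(1 − r²)
- gap: s0² − 2·r·s0·s1 + r²·s1² = (s0 − r·s1)², which is never negative

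With s0 = s1 the ratio of ANCOVA to change-score variance is (1 − r²) / [2(1 − r)] = (1 + r)/2. The standard error falls by 1 − √[(1 + r)/2]. If the change score had 80% power, ANCOVA would have power Φ(2.802/√[(1 + r)/2] − 1.960).

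| r (assumed) | Variance ratio | SE reduction | Power where change score has 80% | Per arm for 80% by ANCOVA |
|---|---|---|---|---|
| 0.3 | 0.65 | 19% | 93.5% | 37 |
| 0.5 | 0.75 | 13% | 89.9% | 42 |
| 0.7 | 0.85 | 8% | 86.0% | 48 |
| 0.9 | 0.95 | 2.5% | 82.0% | 54 |

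The last two columns are illustrations. The plan powers no laboratory or vital-sign contrast.

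**Cost of estimating the slope.** A simulation of 20,000 trials with 56 per arm and normal data gave variance ratios of 0.649, 0.763, 0.863 and 0.958 at the same four correlations. Estimating the slope therefore costs about one percentage point.

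**Unequal SDs.** The gap is zero when s0 = r·s1. Example: r = 0.5, s0 = 0.5, s1 = 1. Change score: 0.25 + 1 − 0.5 = 0.75. ANCOVA: 1 − 0.25 = 0.75. There is no gain.

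**Chance imbalance.** One standard error of the baseline difference is √(2/56) = 0.19 SD. Given such an imbalance and equal SDs, the change-score estimate is displaced by (1 − r) × 0.19 SD in the opposite direction: 0.13, 0.09, 0.06 and 0.02 SD at r = 0.3, 0.5, 0.7 and 0.9. ANCOVA adjusts for this displacement.

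**Within-arm tests.** If both arms have the same true change and each within-arm test has 80% power, exactly one arm is significant with probability 2 × 0.8 × 0.2 = 32%.

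**The case against.** **The planned test is not wrong.** A reader might infer that an unadjusted comparison is biased or has the wrong type I error. It has neither fault: with 1:1 randomisation, an analysis of variance of change is unbiased and valid. This objection stands in full. The point is about efficiency, in a safety section on which no sample size rests.

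**The gain may be small.** The subjects have stable comorbidities controlled by medication, so a high r for the related laboratory values cannot be excluded, and at r = 0.9 the standard error falls by only 2.5%. For hs-CRP, the mild-symptom criterion requires a value below 10 mg/L at entry, while Day 15 is unrestricted. The baseline SD may then be the smaller one, which moves the ratio away from (1 + r)/2 and could bring the gain close to zero. This also stands. It limits the size of the gain but gives no reason to prefer the change score, since the gap (s0 − r·s1)² cannot be negative and estimating the slope costs little.

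**The efficacy link is inferred.** It is tempting to say that a secondary efficacy endpoint will be analysed this way. The documents do not say which laboratory variables form the comorbidity endpoint, and SAP section 6 lists the clinical comorbidity table separately from the laboratory one. SAP 5.4 is the nearest method stated for laboratory change, but no text assigns it to that endpoint. SAP 5.1 adds little, because its paragraph concerns demographics, medical history and physical examination. The missing definition of the endpoint is a separate gap that ANCOVA does not cure.

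**Within-arm p-values.** A reader might infer that these will be offered as evidence of effect. The SAP does not say so, and the same sentence provides the between-arm comparison. What remains is a labelling matter.

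**Conclusion.** The point holds as a minor, free improvement. SAP 5.4 leaves a collected baseline unused as a covariate, and in general this costs precision. With equal SDs, the standard error from ANCOVA would be lower by about 19% at r = 0.3, falling to 2.5% at r = 0.9. The direction is secure: apart from the small cost of estimating the slope, ANCOVA is never less precise than the change score. The size is not secure, because it depends on r and on the ratio of the SDs, neither of which the documents give. The power figures of about 94%, 90%, 86% and 82% describe a hypothetical contrast with 80% power by change score, not anything this plan claims. The documents do not support a finding that the planned test is invalid, that an efficacy endpoint is definitely affected, or that within-arm results will be read as treatment effects.

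**What to change.** - In SAP 5.4, compare arms by ANCOVA of the follow-up value (Day 15, or discharge day if earlier) with arm and baseline in the model. Report the adjusted difference with its 95% CI.
- Analyse skewed laboratory values such as hs-CRP on the log scale. SAP 5.0 plans a Shapiro-Wilk check, but 5.4 names no alternative if it fails.
- State which value is the baseline. For laboratory tests it can only be Screening. For vital signs the SAP must choose between Screening and Day 1.
- Label the within-arm t-tests descriptive, or drop them.
- In SAP 5.3, state that the same model applies to the laboratory part of "Change in clinical or laboratory assessment of comorbid condition", and list the variables it covers.

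The cost is SAP wording and a small change to the analysis program. No new data, visits or subjects are needed.
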